## **7.2 Record Retention**

All source documents, records, and reports will be retained by the clinical center/investigator in accordance with ICH guidelines. These documents include all primary data or copies thereof (eg, laboratory records, ECGs, data sheets, correspondence, photographs, and computer records), which are a result of the original observations and activities of the study and are necessary for the reconstruction and evaluation of any study report.

All source documents, records, and reports should be retained for a period of not less than 15 years from completion of the clinical trial. The sponsor will notify site staff of permission to dispose of them.

## **7.3 Quality Control**

Adverse events and medical histories will be coded using the Medical Dictionary for Regulatory Activities (MedDRA) dictionary.

Medications will be coded to indication-specific ATC (Anatomical Therapeutic Chemical classification) and preferred name using the World Health Organization Drug Dictionary.

The study data will be captured by the investigational site staff on CRFs. The staff will keep records of the subject's visit in the files considered as source documents for that site.

Study information on PN/I.V. infusions and 48-hour I/O will be recorded by the subjects in subject diaries. These data are regarded as source data and will remain at the site. The relevant information will be recorded in the CRF at each study visit.

To ensure that data have been entered correctly on the CRF, they will be 100% source-data verified by a monitor from the sponsor/designee, who will notify the investigator regarding any questions or discrepant data. Data validation and edit checks will be conducted by the sponsor or designee. Any discrepancies noted will generate queries. Upon receipt of the query via the electronic data capture (EDC) system, the site will research the issue identified on the query and record the answer in EDC. In the event that the appropriate individual at the site provides an incorrect, incomplete, or inappropriate response, the query will be re-issued to the site. When all subjects' data have been entered into the database, verified, and all outstanding issues have been resolved with the site, the data will be evaluated for quality purposes. A clean file of the data is defined as when the data in the database and the reference values are complete and logical according to the protocol, general guidelines, and data management plan. Once the sponsor or designee acknowledge that all data are acceptable, the data will be declared a "clean file," and the database will be frozen/hard locked. At the end of the study, each site will receive a compact disc containing their data.

## 8 STATISTICAL METHODOLOGY

### 8.1 Demographic and Baseline Variables

Demographic variables include age; gender; race; height; body weight; BMI; intestinal length; presence or absence of a stoma, colon in continuity, ileocecal valve; and time since last surgical resection.

Descriptive statistics (eg, number, mean, standard deviation, median, minimum and maximum values, and the number and percentage of subjects in specified categories) will be used to summarize the baseline and demographic characteristics. Individual data will also be listed.

### 8.2 Efficacy and Pharmacodynamic Variables

No formal testing will be conducted for efficacy or pharmacodynamic variables. For continuous variables, descriptive statistics will be used to summarize median, maximum, minimum, mean ( $\pm$  standard deviation [SD]), geometric mean ( $\pm$  standard error [SE]) and its 95% confidence interval (CI). For categorical variables n (%) will be summarized. Listings of individual data will be summarized.

PK parameter estimates will be calculated using a non-compartmental analysis.

#### 8.2.1 Efficacy and Pharmacodynamics – Stage 2

The efficacy endpoints are:

- Absolute and percent change from baseline in weekly PN/I.V. volume over 24 weeks (by visits and EOT). Weekly PN/I.V. volume will be based on the subject diary recordings.
- Percentage of subjects who demonstrate a response at Week 20 and again at Week 24 in Stage 2 of the study (responder). A response is defined as the achievement of at least a 20% reduction from baseline (Visit 2) in weekly PN/I.V. volume.
- Change in days per week of PN/I.V. support
- Changes in plasma citrulline from baseline to Week 24 (or EOT)

In this uncontrolled study, efficacy will be described by the following assessments:

- Comparison of the mean PN/I.V. percent change at Week 24 with the upper limit of the 95% CI (of least square [LS] mean) for the teduglutide group in pivotal Phase 3 Study CL0600-020 at Week 24. As Study TED-C14-004 is an uncontrolled study, PN/I.V. results will be compared with those from US/EU pivotal controlled Phase 3 Study CL0600-020. The comparison should take into account the anticipated variability of the data due to the small number of subjects in Study TED-C14-004.
- Comparison of the upper limit of the 95% CI of the mean percent change in weekly PN/I.V. volume at Week 24 with the mean change in PN/I.V. volume at Week 24 in the placebo group in Study CL0600-020. As Study TED-C14-004 is an uncontrolled study, PN/I.V. results will be compared with those from Study CL0600-020. The comparison should take

into account the anticipated variability of the data due to the small number of subjects in Study TED-C14-004.

- Comparison of the mean PN/I.V. percent change at Week 24 with the lower limit of the 95% CI (of LS mean) for the teduglutide group in pivotal Phase 3 Study CL0600-020 at Week 24. As Study TED-C14-004 is an uncontrolled study, PN/I.V. results will be compared with those from US/EU pivotal controlled Phase 3 Study CL0600-020. The comparison should take into account the anticipated variability of the data due to the small number of subjects in Study TED-C14-004.
- Comparison of the responder rate with the primary endpoint responder rate of the placebo group observed in Study CL0600-020. (The percentage of subjects who achieved  $\geq 20\%$  PN/I.V. reduction from baseline at Week 20 and Week 24 in the placebo group was 30.2%).
- Evaluation of the change in days off PN/I.V. per week. In general, day(s) off PN/I.V. cannot be expected in this subject population, which has required long-term PN/I.V., unless absorption is increased by teduglutide.
- Evaluation of the number of subjects who achieve complete enteral autonomy (wean off) of PN/I.V. during the study. In general, weaning off PN/I.V. cannot be expected in this subject population, which has required long-term PN/I.V., unless absorption is increased by teduglutide.

### 8.2.2 Efficacy and Pharmacodynamics – Stages 3 and 4

Absolute and percent change from baseline in weekly PN/I.V. volume and changes in days per week of PN/I.V. support and plasma citrulline levels will continue to be evaluated throughout the long-term extension.

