## **4 SUBJECT SELECTION AND PARTICIPATION**

### **4.1 Number of Subjects**

At least 5 subjects with PN/I.V.-dependent SBS will be enrolled.

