## **8.7 Determination of Sample Size**

The sample size is determined based on the small patient population and the feasibility of the study, rather than power calculation.

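### Section 8.2.1 sets this study's small-sample mean against the pivotal trial's 95% CI limits, a yardstick that leaves out this study's own sampling error and is about three times too narrow at 5 subjects

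*Protocol*

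**What the plan says.** In the current (four-stage) protocol, section 8.2.1 introduces its list with "In this uncontrolled study, efficacy will be described by the following assessments". Two of the bullets concern the teduglutide arm of CL0600-020:

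- "Comparison of the mean PN/I.V. percent change at Week 24 with the upper limit of the 95% CI (of least square [LS] mean") for that arm at Week 24;
- "Comparison of the mean PN/I.V. percent change at Week 24 with the lower limit of the 95% CI (of LS mean") for the same arm and week.

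Both bullets end with the same caution: "The comparison should take into account the anticipated variability of the data due to the small number of subjects in Study TED-C14-004". No method for doing this is given in the protocol.

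Section 8.2 says "No formal testing will be conducted for efficacy or pharmacodynamic variables". On size, section 4.1 says "At least 5 subjects with PN/I.V.-dependent SBS will be enrolled", with no upper bound, and section 8.7 says "The sample size is determined based on the small patient population and the feasibility of the study, rather than power calculation".

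Between the two teduglutide bullets is one on placebo. It uses the upper limit of this study's own 95% CI and sets it against the pivotal placebo mean. The two teduglutide bullets use this study's mean alone, without an interval.

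**The concern.** A 95% CI for the pivotal LS mean says where the pivotal population mean plausibly lies, given the pivotal sample. It is not the range in which the mean of a new sample should fall. That range must also include the new sample's error, and with about 5 subjects this is the larger component by far. Neither teduglutide bullet includes it.

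The study has no control arm, and section 1.2 gives its purpose as evidence of safety and efficacy in Japanese patients. The external comparisons in section 8.2.1 are how efficacy will be described. A mean above the upper limit (a smaller reduction than the pivotal interval covers) may be read as a weaker effect in Japanese patients when it is ordinary sampling noise. A mean inside the limits may be read as closer agreement than a handful of subjects can show.

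A smaller point concerns the type of mean. This study's figure is called a mean and the pivotal one an LS mean. The pivotal model is not described, so the size of any mismatch cannot be judged here.

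**Working it through.** The protocol gives no power, acceptance probability or computed sample size for this comparison, so there is no stated figure to reproduce. The check asks how often a study with the same true effect would fall outside the pivotal limits.

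**Inputs**

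- n = 5, the enrolment minimum (section 4.1); 7 and 10 as alternatives.
- Pivotal arm N. Not stated. Section 1.1 gives a teduglutide responder rate of 62.8% and section 8.2.1 a placebo rate of 30.2%. If both arms share one denominator, only 43 and 86 fit both rates up to 100 (27/43 = 62.8%, 13/43 = 30.2%). N = 43 is assumed.
- Equal true means and equal SDs (assumed). Everything is in SD units, so the unknown SD cancels.

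**Formulas**

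- Half-width of the pivotal CI: h = c/√N. With c = 1.96, h = 1.96/√43 = 0.299. With the t value on 42 degrees of freedom (2.018), h = 0.308.
- SD of the difference between the two means: s = √(1/n + 1/N). At n = 5, s = √(0.2000 + 0.0233) = 0.472.
- Chance of falling outside, both sides: 2 × [1 − Φ(h/s)]. Half of this is above the upper limit, the unfavourable side, because the endpoint is a reduction.

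**Results, N = 43**

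| n | s | h/s (c = 1.96) | Outside, c = 1.96 | Outside, c = 2.018 | Unfavourable side |
|---|---|---|---|---|---|
| 5 | 0.472 | 0.633 | 52.7% | 51.5% | about 26% |
| 7 | 0.408 | 0.733 | 46.3% | 45.0% | about 23% |
| 10 | 0.351 | 0.851 | 39.5% | 38.1% | 19 to 20% |

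A simulation at n = 5 with 200,000 replicates gave 51.8% with normal data and 52.0% with skewed data.

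**Sensitivity at n = 5 (t-based limits)**

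- SD in this study 0.75 times the pivotal SD: 40%. At 1.25 times: 60%.
- N = 39: 50%. N = 86: 64%.
- Pivotal estimate taken as exactly the true effect, so that only this study's mean varies: 49%.

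With N = 43 and n = 20 the figure is still 26%.

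**Width of a suitable reference**

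A 95% range for the difference has half-width c × s: 1.96 × 0.472 = 0.926 SD, or 2.018 × 0.472 = 0.954 SD. Against the pivotal half-width the ratio is s/(1/√N) = √(43/5 + 1) = √9.6 = 3.1. It is 2.7 at n = 7 and 2.3 at n = 10. In simulation, an identical effect missed the 0.954 SD range 5.0% of the time.

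**The case against.** The strongest reply is that a miss rate belongs to a decision rule and the protocol has none. A reader might infer that the two bullets together form a consistency test, so that a mean outside the limits would be declared inconsistent with the pivotal result. The text does not support that. Section 8.2.1 speaks of describing efficacy, section 8.2 rules out formal testing, section 8.6.4 rules out hypothesis testing, and the bullets never mention consistency. This part of the reply stands, and the percentages above measure how misleading the yardstick is, not an error rate of the plan.

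Other parts also stand:

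- The figure of about half counts both directions. A mean beyond the lower limit is a larger reduction, which nothing in the protocol treats as adverse. The chance of appearing worse is about one in four at n = 5.
- N = 43 and equal SDs are assumptions, and 5 is a minimum.
- A prediction interval used as an acceptance criterion would be undemanding. With the same assumptions, a true shortfall of 0.5 SD would land outside it on the worse side only about 18% of the time: Φ((0.5 − 0.926)/0.472) = Φ(−0.90).

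Two parts do not stand. The placebo bullet does use this study's own CI, but for a different question, and it leaves the teduglutide comparison as it is. The sentence on variability could be given a method in the SAP, which is not shown. However, the protocol itself fixes the pivotal limits as the comparator, and a general caution does not widen them.

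**Conclusion.** The point holds as one about the choice of yardstick in a descriptive comparison. The pivotal CI limits are too narrow a reference for a mean of about 5 new subjects, by a factor of about 3.1 if the pivotal arm had 43. With equal true means and SDs, an identical effect lies outside them about 52% of the time at n = 5, with about 26% on the unfavourable side. The figures fall to about 46% at n = 7 and about 40% at n = 10. SD ratios from 0.75 to 1.25 move the n = 5 figure between about 40% and 60%.

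The exact percentages depend on an inferred arm size. The direction does not: the limits omit this study's sampling error whatever N is. It is a worthwhile, inexpensive improvement to how the results are presented. It does not show that the plan will reach a wrong formal conclusion, because the plan reaches none.

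**What to change.** Replace or supplement the two teduglutide bullets with wording such as: the difference in mean percent change in weekly PN/I.V. volume at Week 24 between TED-C14-004 and the CL0600-020 teduglutide group will be presented descriptively, with a 95% CI based on the standard errors of both studies, using the same type of mean in both where available.

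The degrees of freedom should be named. The factor of about three holds with a multiplier near 2. If each study's SD is estimated separately (Welch), there are about 5 degrees of freedom at n = 5 with equal SDs. The multiplier is then 2.57 and the half-width 2.57 × 0.472 = 1.21 SD.

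As an option, show the 95% prediction interval for a mean of n subjects, derived from CL0600-020, as context only and not as an acceptance criterion.

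The cost is a wording change in the protocol and SAP, plus the mean, SD or SE and number of subjects from a completed study. There is no effect on conduct or on subjects. The price is candour: with an interval at least three times wider at n = 5, any statement that the Japanese result resembles the pivotal one will be weaker.

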## 8.3 Safety

The safety and tolerability of teduglutide treatment will be assessed by evaluation of TEAEs, 12-lead ECGs, vital signs, GI-specific testing, laboratory safety data, antibodies to teduglutide, and changes in urine output, body weight, and BMI. See Section 6.2 for a full list of safety variables.

### 8.3.1 Statistical Methods for Safety Variables

Adverse events will be coded using the most recent version of the MedDRA dictionary. Treatment-emergent AEs will be summarized by system organ class and preferred term using descriptive statistics (eg, number and percentage of subjects). Adverse events will be summarized by severity, relationship to treatment, AEs leading to discontinuation, and AEs leading to death. SAEs will also be tabulated by overall and treatment-related events.

For laboratory tests, 48-hour urine output, vital signs, body weight, BMI, and ECG variables, descriptive statistics (eg, n, mean, standard deviation, median, minimum and maximum values, the number and percentage of subjects in specified categories) will be used to summarize the absolute values and change from Baseline at each time point.

The number and percentage of subjects classified as having antibodies to teduglutide will be used to summarize the presence of antibodies.

#### **8.4 Pharmacokinetic Variables – Stage 2 Only**

Single-dose PK will be evaluated on the first day of teduglutide treatment (Day 0). Pharmacokinetic variables include  $AUC_{0-\infty}$ ,  $AUC_{0-t}$ ,  $C_{max}$ ,  $t_{max}$ ,  $t_{1/2}$ ,  $CL/F$ , and  $V/F$ . Pharmacokinetic parameter estimates will be calculated using a non-compartmental analysis.

#### **8.5 Analysis Populations, Data Sets, and Time Points**

##### **8.5.1 Analysis Populations**

The intent-to-treat (ITT) population is defined as any subjects who were enrolled into the study and eligible to enter stage 2. The safety population is defined as the subset of ITT with subjects who received at least one administration of study drug with any safety follow up. The primary population analyzed for efficacy will be the ITT population. An additional per-protocol population analysis may also be performed as secondary/sensitivity analysis. Applicable analysis populations will be defined in the Statistical Analysis Plan (SAP).

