## 8.5 Analysis Populations, Data Sets, and Time Points

### 8.5.1 Analysis Populations

The intent-to-treat (ITT) population is defined as any subjects who were enrolled into the study. The safety population is defined as the subset of ITT with subjects who received at least one administration of study drug with any safety follow up. The primary population analyzed for efficacy will be the ITT population. An additional per-protocol population analysis may also be performed as secondary/sensitivity analysis. Applicable analysis populations will be defined in the Statistical Analysis Plan (SAP).

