##### **8.6.2 Handling of Dropouts or Missing Data**

All subjects enrolled will be included in the analyses. Missing safety parameters will not be imputed. The weekly PN/I.V. volume recorded in the subject diaries will be calculated in 2-week intervals. Missing daily PN/I.V. volumes from subject diaries will not be imputed and a maximum of 5 missing days (or at least 9 days of non-missing data) from the 14-day intervals are allowable, or else the interval will be classified as missing. Details for the imputation algorithm for the missing endpoint values for PN/I.V. volume will be detailed in the SAP.

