##### **8.6.5 Use of an Efficacy Subset of Subjects**

All subjects will be included in the analysis.

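### The safety population is nested inside an eligibility-conditioned ITT set, so a subject dosed without valid eligibility is left out of the safety analysis; Sections 8.6.2 and 8.6.5 were not aligned with that ITT definition.

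*Protocol*

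**What the plan says.** In the current version of the protocol, Section 8.5.1 builds one population inside another. It starts with ITT: "The intent-to-treat (ITT) population is defined as any subjects who were enrolled into the study and eligible to enter stage 2". It continues: "The safety population is defined as the subset of ITT with subjects who received at least one administration of study drug". The membership condition in full is that a subject "received at least one administration of study drug with any safety follow up". So the safety set carries three conditions: eligibility (inherited through ITT), dosing, and some follow-up. For efficacy, "The primary population analyzed for efficacy will be the ITT population". The section leaves a per-protocol analysis optional and ends by pointing to the SAP for the applicable populations.

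Two later sections are worded more broadly. Section 8.6.2, on dropouts and missing data, says "All subjects enrolled will be included in the analyses". Section 8.6.5, on efficacy subsets, says "All subjects will be included in the analysis". Neither mentions eligibility for Stage 2.

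**The concern.** A safety population should follow exposure. Here exposure alone does not qualify a subject: the definition also asks whether the subject should have been exposed. Someone who receives the drug and turns out not to have met the entry conditions is the person whose safety data a reader would want to see, and the definition removes that person.

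The exclusion need not be neutral. The entry criteria bar recent cancer (Section 4.3) and untreated pre-malignant gastrointestinal change (Table 4-1). The adverse events of special interest in Section 6.2.3 are polyp growth and neoplasia. A disqualifying history that surfaces after dosing could therefore belong to a subject with a relevant event. Safety is the first objective named in Section 2, the planned number is very small, and Section 4.4 says that discontinued subjects are not replaced.

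The wording of 8.6.2 and 8.6.5 adds a lesser problem. The protocol does not describe in one consistent way who is analysed.

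**Working it through.** The protocol gives no figure for this point, so there is none to reproduce. Section 8.7 bases the sample size on feasibility, and Section 8.6.4 rules out hypothesis testing. The check is one of definitions, with simple arithmetic for scale.

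**Step 1: the sets.** Write E for enrolled, G for eligible to enter Stage 2, D for dosed at least once, and F for any safety follow-up. From 8.5.1:
- ITT = E and G
- Safety = E and G and D and F
- All treated = D

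The dosed subjects missing from the safety set are those who fail G or fail F.

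**Step 2: can a dosed subject fail G?** The protocol intends not. Inclusion criterion 6 (Section 4.2) requires the investigator's opinion and Medical Monitor approval of stability, and Table 6-2 has criteria 5 and 6 confirmed at baseline. But criterion 6b compares Visit 2 intake and output with the values at entry to stabilization, within ±25%. Visit 2 is Study Day 0, when the first injection is given. Source verification (Section 7.1) is a separate check on data already entered. A dose given on a wrong eligibility call is therefore possible, though it should be rare.

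**Step 3: can a dosed subject fail F?** Hardly. Section 5.2.2 has the first injection supervised and the subject observed for at least 4 hours. That would normally count as follow-up of some kind.

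**Step 4: scale.** The input is the planned minimum of 5 subjects (Section 4.1). Sizes of 7 and 10 are assumptions, since the protocol gives no upper number.
- Share of the safety set lost if one dosed subject is excluded: 1/5 = 20%; 1/7 = 14.3%; 1/10 = 10%.
- If that subject had the only event at n = 5, the reported rate goes from 1/5 = 20% (exact 95% CI 0.5% to 71.6%) to 0/4 = 0%.
- If there were no events, the one-sided 95% upper bound is 1 − 0.05^(1/n). For n = 5 it is 1 − 0.05^(1/5) = 45.1%; for n = 4 it is 1 − 0.05^(1/4) = 52.7%.

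**Step 5: the meaning of enrolled.**
- Narrow sense: Section 4.2 enrols those who meet all criteria. Section 6.2.7 requires a negative pregnancy test at screening and at baseline before enrolment.
- Wide sense: Section 6.2.9 speaks of an enrolled subject being assessed at screening. Section 8.5.1 itself adds eligibility for Stage 2 as a further condition, which would be redundant under the narrow sense.

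Under the narrow sense, 8.6.2 and 8.5.1 nearly agree. Under the wide sense they do not, because Section 3.1 foresees subjects who fail stabilization twice and never reach Stage 2. A superseded version in the same file defined ITT simply as all enrolled subjects, which matched 8.6.2 and 8.6.5. This explains how the mismatch arose, but the mismatch itself lies within the current text.

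**The case against.** The best defence is that eligibility to enter Stage 2 simply means having passed Stage 1. Study drug is given only from Stage 2 onward, so anyone dosed under the protocol has already been judged eligible. No section says that a later finding takes a subject out of ITT or safety, and an optional per-protocol set is the natural place for such findings. Adverse events are also recorded from consent onward and serious ones reported within 24 hours, whatever the analysis population. Finally, 8.5.1 leaves the applicable populations to the SAP.

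Much of this stands. It reduces the problem to subjects dosed in error or on an invalid eligibility call, and it means that their events would be collected. It does not put those subjects into the safety tables, because the definition makes eligibility a condition of membership. The pointer to the SAP does not cure this either: the protocol already fixes the restrictive definition, and a SAP that follows it inherits the gap.

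A reader might infer two stronger claims, and neither is supported.
- **A subject lost right after dosing is necessarily excluded.** This does not follow. The supervised injection and the 4-hour observation would ordinarily meet the follow-up condition.
- **The responder rate has two competing denominators, one including Stage 1 failures.** Section 8.5.1 names ITT as the primary efficacy population, and 8.6.2 deals with missing data rather than defining populations. A Stage 1 failure is never dosed and has no Week 20 or Week 24 value, so counting that person as a non-responder to teduglutide is not a realistic reading.

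**Conclusion.** The point holds in limited form. As written, Section 8.5.1 excludes from the safety analysis any subject who received study drug without being validly eligible for Stage 2. The event is unlikely, but at the planned minimum of 5 subjects one occurrence costs 20% of the safety data. The fall from 20% to 0% in an event rate further assumes that the excluded subject had the only event, so it shows the possible scale and is not a forecast. The follow-up condition has almost no practical effect and no useful function. The mismatch with 8.6.2 and 8.6.5 is real but secondary: it is a matter of alignment and of one word used in two senses. The conclusion rests on a literal reading of 8.5.1; the SAP, which is not shown, may define the sets differently.

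**What to change.** - In 8.5.1, define the safety population as every subject given one or more doses of study drug, independent of ITT membership, eligibility and follow-up.
- Reword 8.6.2 and 8.6.5 to refer to the ITT population for efficacy and the safety population for safety. State that Stage 1 failures are listed only.
- Define enrolled once and use it in that sense throughout.
- Carry the same definitions into the SAP.

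The cost is wording only. No extra data, visits or subjects are needed.
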